APPENDIX G: Follow-up Phone Call Schedule

	7 days before travel	5 days before travel	3 days before travel	1 day before travel
Review all screening questionnaire answers with the participant, perform the pre-travel questionnaire, and provide a reminder for stool sample submission	X	X	X	X
	3 days after travel	5 days after travel	7 days after travel	10 days after travel
Reminder for post-travel questionnaire and stool sample submission	X	X	X	X

APPENDIX H: Promotion Materials

Facebook:

Traveling overseas? Our clinic is offering an opportunity to enroll in a study regarding travelers diarrhea. You'll be compensated for your participation. Check out our website at www.travelhealth.net for more information!

Traveling abroad? Consider enrolling in our study regarding travelers' diarrhea. Visit our website at www.travelhealth.net or schedule an appointment by calling [contact] to learn more!

Participate in our study regarding travelers' diarrhea! If you're interested and have international travel plans, check out our website at www.travelhealth.net for more information.

Twitter (@nyctravelmed):

Traveling abroad? Enroll in our study regarding travelers' diarrhea. More info at www.travelhealth.net. [102 characters]

Make \$ during travel & help us learn more - enroll in a study regarding travelers' diarrhea. Visit www.travelhealth.net! [121 characters]

[figure not shown]
Our clinic is now enrolling for a study regarding travelers' diarrhea. Make \$ and learn more at www.travelhealth.net! [117 characters]

Instagram:

[stock image from public health image library]

Participate in a study regarding travelers' diarrhea! Visit our website at www.travelhealth.net for more info on how to participate!

[stock image from public health image library]

Traveling internationally? Participate in a study regarding travelers' diarrhea and receive compensation for your time! Visit our website at www.travelhealth.net for more info!

Clinic website:

Participate in a Study to Prevent Travelers' Diarrhea

The New York Travel and Tropical Medicine Clinic is now enrolling international travelers in a study of a medication to prevent travelers' diarrhea. Participants will be compensated for their time. If you or someone you know is 18 or older, is traveling internationally in the upcoming months, and is interested in learning more, give us a call or schedule an appointment with a provider.

Newspaper (Manhattan and/or Brooklyn):

Traveling internationally soon?

The New York Travel and Tropical Medicine Clinic is now enrolling international travelers in a study of a medication to prevent travelers' diarrhea. Participants will be compensated for their time! If you or someone you know is 18 or older, is traveling internationally in the upcoming months, and is interested in learning more, give us a call at [contact] to schedule an appointment. Visit us at www.travelhealth.net.

Social media management plan:

1. User comments will be monitored for accuracy weekly
2. For any technical issues regarding posts on Facebook, Twitter, and Instagram, those platforms will be notified of issues. A web management organization assists with the clinic website.
3. Inappropriate or misleading comments will be addressed immediately. Depending on the nature of the comment, it will be addressed in public forum or removed and addressed specifically with the individual who posted the comment.

APPENDIX I: Data Analysis Table Shells

Table 1. Baseline Characteristics of Participants

	BSS	Placebo	P-value
Demographics			
Age			
Sex			
Race			
Ethnicity			
Medical History			
Chronic medical conditions			
Tinnitus			
Antibiotics between 30 to 90 days prior to travel			
Probiotics within 30 days			
Travel			
Duration of travel			
Primary reason for travel			
Secondary reasons for travel			
Attended provider (by type)			

Table 2. Odds ratios (OR) of TD associated with BSS among international travelers, adjusting for select factors

	Total, N	TD, %	OR (95% CI)
Tablets			
BSS			
Placebo			Ref
Age groups, years			
≥18			
Sex			
Male			
Female			Ref
Race/ethnicity			
Travel region			
Travel duration			

Table 3. The proportion of participants having resistance genes before and after travel; acquiring, losing, or maintaining genes after travel

	All participants	BSS	Placebo	P-value
Pre-travel				
Gene 1				
Gene 2				
Gene 3				
Gene 4				
...				
Post-travel				
Gene 1				
Gene 2				
Gene 3				
Gene 4				
...				
Acquisition of gene				
Gene 1				
Gene 2				
Gene 3				
Gene 4				
...				
Loss of gene				
Gene 1				
Gene 2				
Gene 3				
Gene 4				
...				
Maintenance of gene				
Gene 1				
Gene 2				
Gene 3				
Gene 4				
...				

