The active component of BSS with antimicrobial effects is bismuth, which is poorly absorbed and mostly remains in the GI tract while salicylate is systemically absorbed in the stomach (9). The mechanism of action of BSS in the prevention of TD is thought to be due to bismuth's intraluminal antimicrobial properties and a reduction in the number of bacteria (4, 6, 9, 10). In-vitro studies suggest that bismuth's action is bactericidal (6, 11), even at various levels of intestinal pH and against a wide range of organisms (11). The precise mechanisms of action include the binding of ingested bacteria and subsequent marking of these organisms to be killed by host defenses, rendering the bacteria unable to attach to receptor sites that are important for colonization and infection (11), degrading the bacterial cell wall, inhibiting ATP synthesis, and inhibiting the function of the plasma membrane (9). This inhibition may occur in as little as 0.5–24 hours (9). BSS may also inactivate bacterial toxins before attachment to the intestinal mucosa (12). Viruses may be inhibited by BSS; it may prevent viral invasion and deter replication through unknown mechanisms (4).

There is a current domestic and international focus on preventing the acquisition of drug-resistant enteric bacteria by high-risk groups, including travelers (13). International travelers are at increased risk for acquiring gut organisms containing AMR genes (especially after travel to Asia), developing TD, taking antibiotics, and requiring hospitalization (14, 15, 16, 17). Although carriage of organisms containing gut AMR genes may be transient in most travelers (15), it can persist for ≥1 year in over 10% of travelers, increasing the risk of transmission to household members and others (18). Avoiding the use of antibiotics while abroad is one way to lessen acquisition of antibiotic-resistant organisms (19). BSS treatment of adult outpatients with acute diarrhea has been found to reduce antimicrobial medication use in a high prevalence area (20). It is currently unknown whether BSS affects the acquisition of gut AMR genes while traveling abroad; however, given BSS' antimicrobial properties, stability in acidic conditions, and blockage of receptor sites to prevent colonization, it is possible that prophylactic BSS may indirectly prevent acquisition of AMR genes in international travelers by preventing intestinal colonization of ingested microbes. More research must be done to address this uncertainty.

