All travelers who are seen for a pre-travel consultation at The New York Center for Travel and Tropical Medicine will be administered the screening questionnaire by study personnel upon arrival to their consultation to determine their eligibility. Eligible travelers will be invited to participate in the study (see Participant Inclusion / Exclusion Criteria). All participants will be consented as per the protocol (see Procedures for Implementing and Documenting Informed Consent). Randomization of participants will be double-blinded and conducted via block randomization to ensure groups of equal sample sizes using a computer generated distribution. Study medications for both the intervention and placebo group will be provided by P&G, blinded by CDC (using a unique identifier), and distributed to participants at the clinic site during the pre-travel consultation/enrollment visit per the randomization mentioned above (see Study Medications). Study personnel at The New York Center for Travel and Tropical Medicine will not be aware of which medications are BSS or placebo. The code number of the medication (intervention or placebo) administered to a particular participant will be recorded. All code numbers and corresponding arms will be kept secret until the end of the trial.

Web-based questionnaires will be administered during and post-travel (see Study Instruments). Pre-travel data will be collected via telephone with study personnel. Pre-travel data will include information on the participant's medical history and travel plans, and post-travel data will include information on the TD symptoms, medication use, medical care received, and adverse events. During travel, the participant will complete a daily questionnaire that will include data on compliance with taking the study tablets, presence of symptoms of TD, onset of adverse reactions, any medical care received, and trip specifics. The during-travel questionnaire will be made available in both a web-based electronic form and a paper form in the event that the participant does not have reliable internet access. Any paper forms that were completed will be returned by mail

after they return from travel via a pre-paid envelope addressed to the study clinic that was given to the participant when enrolled.

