Includes the 7 days prior to departure in which the pre-travel questionnaire and a biologic (stool) specimen is collected, the full duration of travel, and through 10 days maximum post-return from travel, or until both the post-travel questionnaire and submission of the post-travel biologic (stool) specimen is complete (a maximum of 17 days post-travel)

Travel companion (group):

Two or more study participants with a common relation (friends, colleagues, or relatives) with the same itinerary, who anticipate performing the same activities during travel

Trip duration:

The number of days spent in country; excludes air travel time

Severe TD:

Hospitalization to an inpatient ward either during travel or after travel with a diagnosis of diarrhea

Acquisition of AMR gene(s):

The presence in a post-travel biologic (stool) specimen of one or more antimicrobial resistance gene(s) that were not present in a pre-travel biologic (stool) specimen from the same person, and which is known to confer antimicrobial resistance to one or more antimicrobial agents ("resistome")

Medication compliance:

Full = participant takes all scheduled doses according to directions

Good = If <15% of BSS or placebo doses were missed during travel

Fair = If 15–30% of BSS or placebo doses were missed during travel

Poor = If >30% of doses were missed during travel

Questionnaire compliance:

Full = participant completes all questionnaires

Good = participant completes >80% of all during travel questionnaires, AND
both the pre- and post-travel questionnaires

Fair = participant completes between 30–80% of all during travel
questionnaires, including AT LEAST the pre-travel questionnaire

Poor = participant completes <40% of all during travel questionnaires, and AT
LEAST the pre-travel questionnaire

Biologic (stool) specimen compliance:

Full = BOTH specimens collected and sent

Fair = ONLY one specimen collected and sent

Poor = No specimens collected and sent

Loss to follow-up:

Failure to complete the post-travel questionnaire after three attempts to contact the participant or if submission of the post-travel biologic specimen (stool) occurs more than 10 days after return from travel or is not submitted

Participant Inclusion Criteria

Willing participants must meet the inclusion criteria as outlined here:

1. Be ≥ 18 and <70 years of age at the time of enrollment

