9. Have had diarrhea (see Definitions) anytime in the previous 30 days, have diarrhea at the pre-travel consultation, or develop diarrhea before departure
10. Have been given doxycycline for malaria prophylaxis for the current trip (due to possible drug-drug interactions and decreased absorption of the doxycycline) (27)
11. Have an allergy to any component of the placebo tablets

Estimated Number of Participants

We anticipate enrolling approximately 500 participants (see Sample Size and Power Calculation).

Sample Size and Power Calculation

A sample size of 488 participants with full compliance to medications and questionnaires (244 participants in each arm) is needed to fulfill the objectives [anticipated incidence of the endpoint as 40% incidence of TD with a 30% minimum intervention protection ($0.40-[0.4 \times 0.30] = 0.28$) with an alpha of 0.05, and 80% power].

Recruitment and Enrollment

All international travelers undergo a screening questionnaire at their pre-travel consultation to determine eligibility. This short questionnaire includes questions regarding the travelers' [see **APPENDIX A**]:

1. Age
2. Travel destination(s)
3. Trip duration
4. Acute and chronic medical conditions, including diarrhea
5. Contraindications to BSS administration
6. All current medications, including antibiotic use within the 30 days before screening
7. Willingness to participate in the trial and comply with the data collection requirements

This screening questionnaire will be administered to the traveler by study personnel at The New York Center for Travel and Tropical Medicine. The purpose will be to exclude those travelers who do not meet all inclusion criteria and those who meet any exclusion criteria (see Participant Inclusion / Exclusion Criteria). Travelers who meet the inclusion criteria and do not meet any exclusion criteria will be introduced to the project objectives and procedures, including the procedures for biologic (stool) specimen collection (see Laboratory instruments).

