3. Current medications (including use of probiotics, over-the-counter medications, or herbal supplements)
4. Previous international travel in the past 90 days
5. Travel plans including destination(s) and duration
6. Reason(s) for travel

During Travel (see APPENDIX D)

During travel, participants complete a daily questionnaire that will include the following information:

1. Date, time, and number of study tablets taken (to provide information on the number of missed doses)
2. Presence of gastrointestinal symptoms (e.g., abdominal cramping, fever, nausea, vomiting, tenesmus)
3. Duration of GI symptoms
4. Possible medication adverse reactions (e.g., tinnitus, black stool, etc.)
5. Other illnesses acquired (e.g., upper respiratory infection)
6. Hospital admission or contact with a healthcare facilities or providers or taking any non-routine medications for illness while abroad
7. Countries visited
8. Foods eaten (fermented foods or yogurt)

Details on the participant's trip (number 7 above) are necessary to determine risk factors for the acquisition of gut AMR genes among those participants in the placebo group vs the intervention group.

Web-based data collection will be used to facilitate data collection during travel. Each participant will receive a unique URL to input their

daily information using their unique Study ID and Group ID. A paper copy of the daily travel questionnaire will be provided as a back-up mechanism for data capture where internet access is limited or unavailable. If a participant does not think that they will have reliable internet access while abroad, they will be encouraged to use the paper copies to ensure real-time data collection. Labels will be provided to ensure that the paper copies are de-identified. Any paper forms that were completed will be returned by mail after they return from travel via a pre-paid envelope addressed to the study clinic that was given to the participant when enrolled (see Procedures).

Participants will take either BSS or placebo for the duration of travel, unless they reach a study outcome or criteria for removal (see Outcomes and Criteria for Removal from the Study).

Post-travel (see **APPENDIX E**)

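### The only planned AMR comparison is unadjusted, although the trial collects baseline predictors of acquisition and already adjusts the TD analysis for region and duration

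*Combined protocol and SAP*

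**What the plan says.** Appendix I holds the analysis shells. The AMR shell is "Table 3. The proportion of participants having resistance genes before and after travel; acquiring, losing, or maintaining genes after travel". Its rows are individual genes and its columns are all participants, BSS, placebo and a P-value. The Analytic tests section adds only that changes in the resistome will be compared by treatment. No section gives an adjusted AMR model.

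Appendix I Table 2, for TD, plans adjusted odds ratios with 95% CIs and has rows for travel region and travel duration.

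The protocol treats destination as relevant to AMR. Under Current State of Knowledge it says: "International travelers are at increased risk for acquiring gut organisms containing AMR genes (especially after travel to Asia" (the parenthesis closes there). Under the During Travel questionnaire it says trip details "are necessary to determine risk factors for the acquisition of gut AMR genes among those participants" in the two arms.

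Under Definitions, acquisition means one or more post-travel "antimicrobial resistance gene(s) that were not present in a pre-travel biologic (stool) specimen from the same person". Under Procedures, allocation is by "block randomization to ensure groups of equal sample sizes using a computer generated distribution", with no stratification factor named.

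**The concern.** The plan accepts covariate adjustment for TD and omits it for AMR without giving a reason, although its own background section ties AMR acquisition to destination. Eligible destinations span four regions in Asia and Africa, and randomization is not stated to be stratified by region. Any chance regional imbalance therefore passes into the AMR comparison uncorrected. Appendix I Table 1 has no destination row, so such an imbalance would not even be displayed.

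The covariates needed are pre-dose. Appendix C asks for planned countries and days in each. The pre-travel stool is collected in the 7 days before departure, and the Intervention section starts dosing on the flight before arrival. A gene already present cannot be newly acquired, so the number of genes a participant can still acquire depends on the pre-travel profile.

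At stake is the precision of a secondary objective that has no stated power. There is also a specification risk. The Quality Control section permits interim analysis every 3 months, so an AMR adjustment set chosen later could be criticised as chosen after seeing data.

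**Working it through.** **1. The plan's own figure.** The Sample Size section states "A sample size of 488 participants with full compliance to medications and questionnaires (244 participants in each arm) is needed", based on "anticipated incidence of the endpoint as 40% incidence of TD with a 30% minimum intervention protection" "with an alpha of 0.05, and 80% power". With p1 = 0.40, p2 = 0.28 and mean 0.34, the pooled two-sided formula is

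n = [1.960·√(2·0.34·0.66) + 0.842·√(0.40·0.60 + 0.28·0.72)]² / 0.12² = 243.4, rounded up to 244 per arm, or 488 in total.

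The figure reproduces, with power of 80.1% at 244 per arm. It concerns TD only; no AMR rate, effect or power is given.

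**2. Gain from adjusting for region.** The documents give no acquisition rates by region, so everything below is assumed: a yes/no any-acquisition endpoint, two region strata of equal size (Asia and Africa), and a risk ratio of 0.70 borrowed from the TD sizing.

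- Unadjusted variance term: V_u = p1(1−p1) + p2(1−p2).
- Standardized variance term: V_a = the average over regions of the same expression within region, plus half the between-region variance of the risk difference.
- Share of sample size saved: 1 − V_a/V_u.

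Example with placebo rates of 60% and 20%:
- V_u = 0.2400 + 0.2016 = 0.4416.
- Within-region average = ½(0.2400 + 0.2436) + ½(0.1600 + 0.1204) = 0.3820.
- The regional risk differences are 0.18 and 0.06, with variance 0.0036; half is 0.0018.
- V_a = 0.3838 and the saving is 1 − 0.3838/0.4416 = 13.1%.

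| Assumed placebo rates, Asia/Africa | Gap (points) | Saving, 50:50 split | Saving, 70% to Asia |
|---|---|---|---|
| 45/35% | 10 | 0.8% | 0.7% |
| 50/30% | 20 | 3.3% | 2.6% |
| 60/20% | 40 | 13.1% | 10.3% |
| 70/30% | 40 | 12.1% | 10.0% |
| 80/20% | 60 | 27.2% | 22.7% |

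**3. Power.** For an assumed overall 40% vs 28% AMR contrast with a 50:50 split, unpooled variance:

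| Per arm | Unadjusted | Adjusted, 50/30% | Adjusted, 60/20% |
|---|---|---|---|
| 244 | 80.5% | 81.8% | 85.7% |
| 125 | 52.4% | 53.7% | 58.1% |

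The 125 per arm reflects the laboratory budget (Table 5), which costs stool testing for 250 participants. The Analytic tests section says all kit specimens will be tested, so both sizes are shown.

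**4. Single genes and ceiling.** A simpler approximation ignores the treatment effect: variance share = ((pA − pF)/2)² / [p(1−p)], where pA and pF are the Asia and Africa rates and p is their mean. For assumed per-gene rates of 10% vs 5% it is 0.000625/0.069375 = 0.9%. For 20% vs 10% it is 0.0025/0.1275 = 2.0%. If acquiring at least one gene is near universal, say 95% vs 85%, it is 0.0025/0.09 = 2.8%.

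**5. Chance imbalance.** With 125 per arm and half going to Asia, the between-arm difference in Asia share has SD √(2·0.25/125) = 6.3 points. With a 40-point regional gap and no treatment effect, one SD of imbalance moves the AMR difference by 0.063 × 40 = 2.5 points. The unadjusted standard error is √(2·0.24/125) = 6.2 points, and it already includes this variation.

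**The case against.** Four objections have force.

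- **Bias.** A reader might infer that an Asia/Africa imbalance could pass for a BSS effect. Under randomization the unadjusted test keeps its type I error, and chance imbalance is already in its standard error (step 5). What remains is that, once an imbalance has occurred, an adjusted estimate corrects for it and the raw one does not.
- **Size.** A reader might infer a large loss. Assumed rates of 75% vs 40% or 80% vs 30% give variance shares of 12.5% and 25%, equivalent to about 36 and 84 extra participants on 250. Those figures need an aggregate mid-range endpoint and gaps of 35–50 points. The documents give no regional rates and no numerical Asia–Africa contrast, and the Appendix I Table 3 rows are single genes, where the gain is far smaller. The 250 is also not settled within the documents.
- **Baseline already used.** Acquisition is defined against each participant's own pre-travel specimen, and Table 3 has pre-travel, loss and maintenance rows. That is correct. Only baseline gene burden as a covariate is unused, and the documents do not allow its value, or that of duration, to be quantified.
- **Modelling.** Adjustment cannot be specified without a single outcome and effect measure. A conditional odds ratio is non-collapsible, so its standard error is not comparable with the unadjusted one. Per-gene models could separate when genes are sparse. These points stand and shape the fix.

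The stated aim of examining trip-related risk factors does not close the gap, because no model, covariate list or adjusted treatment estimate follows from it.

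**Conclusion.** The point holds as a gap in efficiency and specification. The AMR comparison leaves out pre-dose predictors that the plan collects, one of which it names as a driver of acquisition, while the TD comparison adjusts for region and duration. The unadjusted test is valid.

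Under the stated assumptions, the gain from region alone is about 1–3% of the sample size for regional gaps of 10–20 points and about 10–13% for 40 points. It could be larger only with very wide gaps, and it is smaller for rare genes or near-universal acquisition. Adjustment does not by itself give the secondary objective adequate power: at 125 per arm and an assumed 40% vs 28% contrast, power moves from 52.4% to between 53.7% and 58.1%. The case for the change is that it needs no new data and fixes the analysis in advance.

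**What to change.** Add one prespecified AMR comparison to Appendix I, settled before any AMR data are examined by arm:

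- **Outcome:** acquisition of one or more AMR genes, yes/no, as defined under Definitions.
- **Covariates:** planned region (the four inclusion regions, with a stated rule for itineraries covering more than one), planned in-country duration (from the days per country in Appendix C), and number of panel genes in the pre-travel specimen. Use planned rather than actual travel, so that every covariate precedes dosing. The gene count is available for everyone whose outcome can be determined, since the outcome needs the same specimen.
- **Estimate:** standardized risk difference (or ratio) for BSS vs placebo with 95% CI, as the result for the secondary objective.
- **Table 3:** keep the per-gene table as descriptive.

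Adding a planned-region row to Appendix I Table 1 would also show any imbalance. The cost is minor extra programming; no new data, visits or participants are needed.
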